6.10.2 Imputation Rules for Incomplete Dates

Missing primary and secondary efficacy endpoints will be handled by Last Observation Carried Forward (LOCF) for continuous variables. More details are provided in the relevant sections for those endpoints (Sections 6.4.1 and 6.4.2).

As a general principle, no imputation of missing data for other variables will be done. Exceptions are the start dates of AEs and start and stop dates of concomitant medication. The imputed dates will be used to allocate the concomitant medication and AEs to a treatment group, in addition to determining whether an AE is/is not treatment emergent. Listings of the AEs and concomitant medications will present the actual partial dates; imputed dates will not be shown.

Values (visit 7/week 12) for certain safety variables (lab values, vital signs values and ECG) and the go-to-bed time for Sunday (eDiary) will be imputed, see below. For calculation of percentiles the not collected day of birthday, in the eCRF, will be imputed.

6.10.2.1 Imputation Rules for Diary Dates

The go-to-bed time for Sunday is not captured in the diary. This time will be imputed as occurring a short time after the second (evening) SBPM was performed: time of second SBPM plus 1 hour. If there is no time entered in the diary for the evening SBPM, then the go-to-sleep time will be imputed as 23:59 (on Sunday), see Section 5.

6.10.2.2 Imputation Rules for Adverse Events

For AEs, a missing or incomplete onset date will be imputed according to the following conventions.

If an onset date is missing or only the year is known, the imputed onset date will be the date of first dose of study drug.

If only the year is known for the AE onset date, the imputed onset date will be the latest of the following non-missing dates:

- Date of first dose of study drug
- January 1 of the year of AE onset date

If only the month and year is known for the onset date, set the surrogate onset date to the first day of that month and then apply the following rules.

- If the month and year of the onset date is prior to the month and year of the first dose of study drug, then the surrogate onset date will be the imputed onset date.
- If the month and year of the onset date is on or after the month and year of the first dose of study drug, then the imputed onset date will be the latest of the following non-missing dates:
 - Date of first dose of study drug
 - Surrogate onset date

If the imputed onset date is after the adverse event end date, the imputed onset date will be the same as the adverse event end date.

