5.4.1 Adverse Events

AEs will be coded using MedDRA. A TEAE is defined as an AE observed after starting administration of the IP until 30 days after the final administration of IP.

If the adverse event occurs on Day 1 and the onset check box on the (AE) eCRF is marked "Onset after first dose of study drug" or the onset check box is left blank, then the adverse event will be considered treatment emergent. If the adverse event occurs on Day 1 and the onset check box is marked "Onset before first dose of study drug", then the adverse event will not be considered treatment emergent. If a subject experiences an event both during the pre-investigational period and during the investigational period, the event will be considered as TEAE only if it has worsened in severity (i.e., it is reported with a new start date).

A drug-related TEAE is defined as any TEAE with at least a possible relationship to study treatment as assessed by the investigator or with missing assessment of the causal relationship.

An AE designated as serious by either the investigator or determined by Important Medical Event process will be summarized as an SAE. However, if the event is on IME list but medical monitor agrees with investigator that event is not SAE, then event can be downgraded.

Common TEAEs are defined as preferred terms (PTs) that have been reported by at least 5% of the subjects in any of the treatment groups.

When an AE start or stop date is missing, the date will be imputed using the rules in Section 6.10.2.2.

Adverse Events of Special Interest

Adverse Events of Special Interest include:

• Abnormal cardiac electrophysiology (including QTc prolongation), cardiac arrhythmia, and other cardiovascular adverse events

- Increased blood pressure as assessed through vital signs monitoring
- Hypersensitivity reactions
- Urinary retention
- Abnormal nervous system events: seizure, syncope, headache and dizziness

AEs of interest will be identified using all Preferred Terms (PT) from Standardized MedDRA queries (SMQ), see Table 2, or sponsor-defined list of search terms, see Appendix 9.2. Note: Most recent MedDRA version in which the AEs are coded will be used.

CV - Increased blood pressure	Hypertension SMQ – Narrow search
CV - QT prolongation	Torsade de pointes/QT prolongation SMQ – Broad search

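### SAP 6.10.2.2 gives two rules for an adverse event dated only by year, and both move an event from a year before dosing to the first-dose date

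*SAP*

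**What the plan says.** SAP 6.10.2 states that imputed dates are used to allocate adverse events to a treatment group, "in addition to determining whether an AE is/is not treatment emergent". Listings show the actual partial dates, not the imputed ones.

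SAP 6.10.2.2 then gives these rules for onset dates:

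- Rule 1: "If an onset date is missing or only the year is known, the imputed onset date will be the date of first dose".
- Rule 2: "If only the year is known for the AE onset date, the imputed onset date will be the latest of the following non-missing dates". The two candidates are the first-dose date and "January 1 of the year of AE onset date".
- Month-and-year rule: a surrogate onset is set to the first day of the month. A separate branch begins "If the month and year of the onset date is prior to the month and year of the first dose of study drug", and in that branch the surrogate is kept, so the event stays before dosing.
- End-date cap: "If the imputed onset date is after the adverse event end date, the imputed onset date will be the same as" the end date.

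SAP 5.4.1 defines the classification: "A TEAE is defined as an AE observed after starting administration of the IP until 30 days after the final administration of IP". A Day 1 event is not treatment emergent if its onset box is marked as before first dose. If the box is marked as after first dose, "or the onset check box is left blank, then the adverse event will be considered treatment emergent". An event experienced in both the pre-investigational and investigational periods counts only if it worsened.

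**The concern.** There are two defects, and they arise in different cases.

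First, rules 1 and 2 both cover an onset of which only the year is known, and they do not give the same date. Nothing says which prevails, so the programmer has to choose.

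Second, neither rule has a branch for an onset year earlier than the year of first dose. Moving an onset to the first-dose date is reasonable when its timing relative to dosing is unknown. Here it is known: an event from an earlier calendar year began before dosing. The month-and-year rule respects that information and the year-only rules discard it.

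At stake is the count of treatment-emergent events. Protocol 7.3.1 collects events from consent, so screening-period events are in the database, and the imputed onset feeds their classification.

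**Working it through.** No sample size, power or error rate is involved. The check applies the rules of SAP 6.10.2.2 and 5.4.1 in sequence.

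**Rules as formulas**

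- Rule 1: imputed onset = first dose.
- Rule 2: imputed onset = max(first dose, January 1 of onset year).
- Cap: if the imputed onset is after the end date, use the end date.
- TEAE: first dose ≤ imputed onset ≤ last dose + 30 days, except that a first-dose-day onset with the box marked before is not a TEAE.

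**Illustrative dates (assumed).** With 84 days of dosing, a first dose on 11 Jan 2021 gives a last dose on 4 Apr 2021, and a first dose on 15 Nov 2021 gives a last dose on 6 Feb 2022. The worsening rule is left out of the table because the SAP does not say how it combines with an imputed date.

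| First dose | Onset year | End date | Box | Rule 1 | Rule 2 | TEAE |
|---|---|---|---|---|---|---|
| 11 Jan 2021 | 2020 | none | blank | 11 Jan 2021 | 11 Jan 2021 | yes, both |
| 11 Jan 2021 | 2020 | 21 Jan 2021 | blank | 11 Jan 2021 | 11 Jan 2021 | yes, both |
| 11 Jan 2021 | 2020 | 6 Jan 2021 | blank | 6 Jan 2021 | 6 Jan 2021 | no, both |
| 11 Jan 2021 | 2020 | none | before | 11 Jan 2021 | 11 Jan 2021 | no, both |
| 15 Nov 2021 | 2022 | none | blank | 15 Nov 2021 | 1 Jan 2022 | yes, both |

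For comparison, an event dated December 2020 with first dose on 11 Jan 2021 falls under the month-and-year rule. It is imputed to 1 Dec 2020 and is not a TEAE. The same event with the month missing, no end date and a blank box is a TEAE.

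**When the two rules differ.** If the onset year is the dosing year or earlier, January 1 of that year is not after first dose, so rule 2 reduces to rule 1. They differ only when the onset year is later.

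**Whether that difference changes TEAE status.** Protocol 7.3.1 collects events until 30 days after final dosing, which is also where the TEAE window ends. For a later-year onset inside the collection period:

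first dose < January 1 of onset year ≤ true onset ≤ last dose + 30 days.

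Both imputed dates therefore lie in the window and both give a TEAE. (A record with a later onset year and the box marked before would contradict itself.)

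**Exposure to the prior-year error.** A subject is exposed only if screening crosses January 1. SAP 6.10.1 gives a maximum of 4 weeks. Assuming even accrual over the year:

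- 28/365 = 7.7%. Of 184 children that is 184 × 28/365 ≈ 14; of 32 adolescents, 32 × 28/365 ≈ 2.5.
- Adding the 3-day early allowance for visit 1 in the Schedule of Assessments: (28 + 3)/365 = 8.5%, or about 16 children and 3 adolescents.

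These are subjects exposed, not events misclassified. Misclassification also needs an event from the earlier year with the month missing, no end date before first dose, and a box that is blank or marked after. The documents give no frequency for any of these.

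**The case against.** The strongest defence is that the SAP has three safeguards. The end-date cap pulls back any event that ended before first dose. The onset box removes an event that the site marked as before first dose. The worsening rule in SAP 5.4.1 shows that the intent is not to count a pre-existing event that merely continues past first dose. In addition, sites ask about adverse events at each visit or call during a roughly 4-week screening period, so losing even the month should be rare. The actual partial dates stay visible in the listings.

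Most of this stands, and it limits the point. It does not remove it. An event that is ongoing or has no recorded end date escapes the cap. The SAP does not say whether the onset box is completed for a partial date, and a blank box leads to a TEAE. The worsening rule depends on recognising a pre-dose onset, whereas SAP 6.10.2 says that the imputed date determines treatment emergence. Which of the two prevails is not stated.

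A reader might infer that one record could be in or out of the TEAE tables depending on which year-only sentence is programmed. For onsets inside the collection period the inequality above rules that out. It could happen only for an event starting after collection ends, such as a related event that the investigator learns of later (Protocol 7.3.3). Allocation to treatment group is not at risk either, because the arms are parallel.

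**Conclusion.** The point holds and is minor. The two year-only rules overlap and conflict, but the conflict affects only later-year onsets and does not change TEAE status for events with onset inside the collection period. The substantive error lies in what the rules share: an event known to precede dosing is dated to first dose and, unless the end date, the onset box or the worsening rule intervenes, is counted as treatment emergent.

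The number affected is likely very small. About 8% of subjects are exposed, assuming even accrual and 28-day screening. A baseline visit postponed for infection or constipation would lengthen screening for the few subjects concerned.

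Two stronger readings should not be drawn. One is that every prior-year event certainly becomes a TEAE, or that 8% of subjects are misclassified; the safeguards and the further conditions above contradict this. The other is that such events would be attributed to the drug. Treatment emergence is a matter of timing, and causality is a separate investigator assessment in SAP 5.4.1.

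**What to change.** In SAP 6.10.2.2:

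1. Remove the year-only clause from the first rule, so that it covers only a completely missing onset date.
2. In the year-only rule, add a branch: if the onset year is before the year of first dose, impute December 31 of that year, subject to the end-date cap, and classify the event as not treatment emergent. Otherwise use the later of the first-dose date and January 1 of the onset year, as now.

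The cost is a short wording change and about one line of code. No new data are needed. SAP section 1 allows revisions before database hard lock, so the change can be made then.

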6.10.2.3 Imputation Rules for Concomitant Medications

In case of missing partial start and stop dates for concomitant medications, the following rules will be used:

If the start date is missing or partial:

- if the month is missing, use January
- if the day is missing, use the first day of the month under consideration
- if the year is missing, use year of the informed consent date
- if the entire date is missing, use informed consent date

If the stop date is missing or partial:

- if the month is missing, use December
- if the day is missing, use the last day of the month under consideration
- if the year or the entire date is missing, set the stop date to December 31st, 2099

If the imputed start date is after the stop date, then the imputed start date will be 1 day prior to the stop date.

6.10.2.4 Imputation Rules for Missing Safety Variables (Lab values, Vital Signs, ECGs or PVR)

In case subject safety data of lab values, vital signs, PVR or ECGs at EoT (visit 7/week 12) is missing, the LOCF method will be used for the summaries or shifts from baseline to EoT only. No values at baseline and no data from more than 5 days after the last dose of study medication will be carried forward to post-baseline visits.

6.10.2.5 Imputation of Age in Months

For the calculation of percentiles of height and weight the age in months is required. Since we capture in the eCRF for birthday only the month and year and not the day, the 15th of the month will be imputed for day.

6.10.3 Outliers

All values will be included in the planned analyses. A sensitivity analysis excluding outliers may be performed as an additional secondary analysis, if considered appropriate by the study statistician or the medical expert.

7 **REVISION AND RATIONALE**

7.1 List of Changes in SAP Version 2.0 from Version 1.0

The changes from the approved SAP Version 1.0 (Dated 07-Aug-2020) to Version 2.0 that impact analyses are listed with the rationale in the table below.

SAP	Description	Rationale	
Section			
2.1	Secondary Objective regarding PK analysis updated	To be consistent with protocol	
	Exploratory Objective: age group is added and endpoint "mean number of micturitions per 24 hours" is added to list of endpoints.	To be consistent with protocol	
2.3	Text added at the end of the paragraph	Text added for clarification	
3	Text is added to state that the assumptions about sample size, in addition to the levels for Type-1 error and power, were agreed upon with Pediatric Committee in the current Pediatric Investigation Plan.	This update is made for clarification of assumptions.	
5.4.1	Text regarding TEAEs updated to reflect text in protocol.	Text differed from the text in protocol.	
	"In any of the treatment groups" is added to "Common TEAEs are defined as preferred terms (PTs) that have been reported by at least 5% of the subjects"	To be in agreement with other studies	
5.5.2	Weight categories in the 2 tables are updated	To be consistent with protocol. The minimum weight of subjects is changed from 11 kg to 13 kg	
6.4.1.4	Added section on scoring by caregiver and subject	To perform a descriptive analysis to investigate the effect of scores by caregiver and subject differ.	
6.4.1.5	Added "Symptomatic UTI" as subgroup	To be consistent with protocol. This was added in version 2 of the protocol	
6.4.3	Added Mean Number of Micturitions per 24 hours as exploratory endpoint	To be consistent with protocol. This endpoint was added in version 2 of the protocol	
6.5.2.1	Added section on Central and Local Laboratories	Lab data can also come from local laboratories, version 2 of protocol.	
6.5.7	Subgroup analyses also done for vital signs.	Vital signs was missing	
	Added Symptomatic UTI as subgroup	To be consistent between efficacy and safety analyses	
6.10.1	Table 10: Day $2 \rightarrow$ Day 1	Subject may stop treatment on the day of the first administration of study drug	
6.10.2	The time to-go-to sleep on Sunday is not captured on the eDiary	To describe here that this missing time will be imputed. Imputation also described in Section 5 of SAP	

7.2 List of Changes in SAP Version 3.0 from Version 2.0

The changes from the approved SAP Version 2.0 (dated 24-Sep-2021) to Version 3.0 that impact analyses are listed with the rationale in the table below.

SAP	Description	Rationale			
Section					
2.1	Secondary efficacy variable "Mean number of nighttime incontinence episodes per 24 hours" was deleted	Endpoint will no longer be analyzed due to changes in inclusion and exclusion criteria			
	Exploratory Endpoints. The following exploratory endpoints are added:	To be in line with previous studies			
	 Mean number of micturitions per 24 hours, adjusted for fluid intake: Number of micturitions per 24 hours that would be required at week 12/EoT to void the same total volume as voided at baseline 				
	 Difference in mean number of micturitions per 24 hours adjusted for fluid intake compared to the expected mean number 				
	• Mean volume voided per micturition as a percentage of expected bladder capacity				
	• Categorized mean volume voided per micturition as a percentage of expected bladder capacity (results and changes from baseline).				
	Added exploratory endpoint: "Change from baseline at the end of the 12-week treatment period (adolescents only) in Maximum Volume Voided"	To correct an omission. In previous version this end-point was only mentioned for children.			
4.5.1	Eligibility Deviations: Inclusion criterion 16 has been removed	Not part of ICCS criteria; unduly restrictive for enrollment			
	Exclusion criterion 1 has been removed	Not part of ICCS criteria; unduly restrictive for enrollment			
	Exclusion criteria 3 and 27 have been removed	No reason to exclude these subjects as monosymptomatic enuresis is known to co-occur with OAB			
5.4.2.3	For calculations reference is made to Center for Disease Control and Prevention website	Using validated SAS® code			
5.2.1	Derivation of mean volume voided was corrected.	Derivation was not correct			
Table cont	ple continued next page				

SAP	Description	Rationale	
Section			
5.2.5	Text in paragraph was updated	For clarification	
5.4.1	An AE designated as serious by either	Sentence was added for further clarification	
	the investigator or determined by	regarding the process.	
	Important Medical Event process will		
	be summarized as an SAE.		
	This paragraph was added with		
	"However, if the event is on IME list		
	but medical monitor agrees with		
	investigator that event is not SAE, then		
	event can be downgraded."		
5.4.5 and	Deletion of text with respect to External	No external ECG data will be collected	
9.5	ECG data and Abnormal ECGs		
6.2.3	Summaries for percentiles of height and	Using validated SAS® code.	
	weight, with respect to age and sex, will		
	be provided using SAS code and dataset		
	Browention website		
61131	Description for a (nonparametric)	To present a nonparametric estimate of the	
0.4.1.3.4	estimate for the difference between	treatment difference	
	placebo and mirabegron with		
	associated (asymptotic) 90% CI was		
	added		
6.4.1.4	Definition of valid diary for caregiver	For clarification and was missing in	
	and for subject was added	previous version	
6.4.3	Text on mean number of micturitions	For clarification	
	per 24h adjusted for fluid intake was		
	updated		
6.5.1	Text regarding "Sponsor's list of	New process: IME	
	Always Serious terms" was updated by		
	adding "or upgraded according to the		
	Important Medical Event process".		
6.5.3	Blood pressure will also be presented by	As suggested by FDA	
	age groups 5 - <8 and 8 - <12 years of		
	age		
6.5.3.2	Calculation of SBPM values added	For clarification	
6.5.6.2	Section of Body Weight and Height was	Missing in previous version	
6 10 1	added	Missing in anovious vonsion	
0.10.1	Analysis window for PVR volume	Missing in previous version	
	Table 10: for SDDM the remerith East	No SDDM assessment along of for End of	
	Table 10: for SBPM the fow with EoS	No SBPM assessment planned for End of Study, but one for with signs	
	added for vital signs	Study, but one for vital signs	
61024	Imputation of missing PVR Volume	To be in line with other variables	
0.10.2.4	was undated	To be in fine with other variables	
Table cont	inued next page	1	

SAP	Description	Rationale
Section		
6.10.2.5	For birthday, only the month and year are captured, and not the day. If day is needed for calculations the 15 th of the month will be imputed for day	Added because for some calculations the day of birthday is needed
8	List of references was updated	Two new references added and one removed.
9.1	Table which presents not allowed medication is deleted. Reference is made to Table 12.6 in protocol.	New table is presented in protocol
9.3	Appendix 9.3 Calculation of Z-score for height by age and sex has been removed	For calculation of Z-score the SAS code and dataset stored on website from Center for Disease Control and Prevention will be used
9.8 and 9.9	Names and titles updated	New titles and contributors/approvers

9 APPENDICES

9.1 Example of SAS Code for Nonparametric ANCOVA

As sensitivity analysis for the primary efficacy endpoint a nonparametric ANCOVA on ranktransformed data (changes from baseline) will be performed (stratified rank ANCOVA). The p-value of the treatment difference will be assessed using a rank ANCOVA stratified by region, see Section on Sensitivity Analysis for Primary Efficacy Endpoint.

The SAS code used to implement this test will be similar to that shown below:

** Ranks within each region will be derived across the two treatment groups for the baseline value (base) and the change from baseline value (chg) stored in the SAS dataset called ranks; PROC RANK NPLUS1 TIES=MEAN OUT=ranks DATA=dataset;

BY Region; RANKS Base_r Chg_r; VAR Base Chg; RUN;

```
** Linear regression models will be applied to these ranks by region;
PROC REG DATA=ranks NOPRINT;
BY Region;
MODEL Chg_r = Base_r Sex;
OUTPUT OUT = residual R = Resid;
RUN;
```

```
** The p-value will be assessed using the stratified mean score test:
PROC FREQ DATA=residual;
TABLES Region*Sex*Trt*Resid / CMH2 noprint;
ODS OUTPUT CHM = outp;
RUN;
```

9.2 AEs of Interest not covered by Standard MedDRA SMQs latest Version

The following is a list of AE terms to programmatically flag subjects with AE's of interest (see Section 5.4.1).

Туре	Term	Code	AE of Interest	MedDRA 24.0 or Higher Search Criteria
LLT	Acute retention of urine	10001055	Acute urinary retention	Selected LLT (non-SMQ)
PT	Residual urine volume	10050832	Urinary retention	Selected PT's (non-SMQ)
PT	Residual urine volume increased	10067758	Urinary retention	Selected PT's (non-SMQ)
PT	Urinary retention	10046555	Urinary retention	Selected PT's (non-SMQ)

Note: Most recent MedDRA version in which AEs are coded will be used.

9.3 2017 American Academy of Pediatric Clinical Practice Guidelines

From 2017 (American Academy of Pediatric) Clinical Practice Guidelines, Table 4, Males, see Reference Flynn, et al, 2017

		Systolic Blood Pressure (mmHg)							Diastolic Blood Pressure (mmHg)						
Age	BP	Percentiles							Percentiles						
(years)	Percentile	5 th	10 th	25 th	50 th	75 th	90 th	95 th	5 th	10 th	25 th	50 th	75 th	90 th	95 th
5	Height (cm)	104.4	106.2	109.1	112.4	115.7	118.6	120.3	104.4	106.2	109.1	112.4	115.7	118.6	120.3
	90 th	103	104	105	106	107	108	108	63	64	65	65	66	67	67
	95 th	107	108	109	109	110	111	112	66	67	68	69	70	70	71
	95th+12mmHg	119	120	121	121	122	123	124	78	79	80	81	82	82	83
6	Height (cm)	110.3	112.2	115.3	118.9	122.4	125.6	127.5	110.3	112.2	115.3	118.9	122.4	125.6	127.5
	90 th	105	105	106	107	109	110	110	66	66	67	68	68	69	69
	95 th	108	109	110	111	112	113	114	69	70	70	71	72	72	73
	95th+12mmHg	120	121	122	123	124	125	126	81	82	82	83	84	84	85
7	Height (cm)	116.1	118	121.4	125.1	128.9	132.4	134.5	116.1	118	121.4	125.1	128.9	132.4	134.5
	90 th	106	107	108	109	110	111	111	68	68	69	70	70	71	71
	95 th	110	110	111	112	114	115	116	71	71	72	73	73	74	74
	95th+12mmHg	122	122	123	124	126	127	128	83	83	84	85	85	86	86
8	Height (cm)	121.4	123.5	127	131	135.1	138.8	141	121.4	123.5	127	131	135.1	138.8	141
	90 th	107	108	109	110	111	112	112	69	70	70	71	72	72	73
	95 th	111	112	112	114	115	116	117	72	73	73	74	75	75	75
	95th+12mmHg	123	124	124	126	127	128	129	84	85	85	86	87	87	87
9	Height (cm)	126	128.3	132.1	136.3	140.7	144.7	147.1	126	128.3	132.1	136.3	140.7	144.7	147.1
	90 th	107	108	109	110	112	113	114	70	71	72	73	74	74	74
	95 th	112	112	113	115	116	118	119	74	74	75	76	76	77	77
	95th+12mmHg	124	124	125	127	128	130	131	86	86	87	88	88	89	89
10	Height (cm)	130.2	132.7	136.7	141.3	146.9	150.1	152.7	130.2	132.7	136.7	141.3	146.9	150.1	152.7
	90 th	108	109	111	112	113	115	116	72	73	74	74	75	75	76
	95 th	112	113	114	116	118	120	121	76	76	77	77	78	78	78
	95th+12mmHg	124	125	126	128	130	132	133	88	88	89	89	90	90	90
11	Height (cm)	134.7	137.3	141.5	145.4	151.3	155.8	158.5	134.7	137.3	141.5	145.4	151.3	155.8	158.5
	90 th	110	111	112	114	116	117	118	74	74	75	75	75	76	76
	95 th	114	114	116	118	120	123	124	77	78	78	78	78	78	78
	95th+12mmHg	126	126	128	130	132	135	136	89	90	90	90	90	90	90
12	Height (cm)	140.3	143	147.5	152.7	157.9	162.6	165.5	140.3	143	147.5	152.7	157.9	152.6	165.5
	90th	113	114	115	117	119	121	122	75	75	75	75	75	76	76
	95th	116	117	118	121	124	126	128	78	78	78	78	78	79	79
	95th+12mmHg	128	129	130	133	136	138	140	90	90	90	90	90	91	91
Sponsor: APGD ISN/Protocol 178-CL-204

		Systolic Blood Pressure (mmHg)				Diastolic Blood Pressure (mmHg)									
Age	BP	Percentiles				Percentiles									
(years)	Percentile	5 th	10 th	25 th	50 th	75 th	90 th	95 th	5 th	10 th	25 th	50 th	75 th	90 th	95 th
5	Height (cm)	103.6	105.3	108.2	111.5	114.9	118.1	120	103.6	105.3	108.2	111.5	114.9	118.1	120
	90 th	104	105	106	107	108	109	110	64	65	66	67	68	69	70
	95 th	108	109	109	110	111	112	113	68	69	70	71	72	73	73
	95th+12mmHg	120	121	121	122	123	124	125	80	81	82	83	84	85	85
6	Height (cm)	110	111.8	114.9	118.4	122.1	125.6	127.7	110	111.8	114.9	118.4	122.1	125.6	127.7
	90 th	105	106	107	108	109	110	111	67	67	68	69	70	71	71
	95 th	109	109	110	111	112	113	114	70	71	72	72	73	74	74
	95th+12mmHg	121	121	122	123	124	125	126	82	83	84	84	85	86	86
7	Height (cm)	115.9	117.8	121.1	124.9	128.8	132.5	134.7	115.9	117.8	121.1	124.9	128.8	132.5	134.7
	90th	106	106	107	109	110	111	112	68	68	69	70	71	72	72
	95th	109	110	111	112	113	114	115	72	72	73	73	74	74	75
	95th+12mmHg	121	122	123	124	125	126	127	84	84	85	85	86	86	87
8	Height (cm)	121	123	126.5	130.6	134.7	138.5	140.9	121	123	126.5	130.6	134.7	138.5	140.9
	90 th	107	107	108	110	111	112	113	69	70	71	72	72	73	73
	95 th	110	111	112	113	115	116	117	72	73	74	74	75	75	75
	95th+12mmHg	122	123	124	125	127	128	129	84	85	86	86	87	87	87
9	Height (cm)	125.3	127.6	131.3	135.6	140.1	144.1	146.6	125.3	127.6	131.3	135.6	140.1	144.1	146.6
	90 th	108	108	109	111	112	113	114	71	71	72	73	73	73	73
	95 th	112	112	113	114	116	117	118	74	74	75	75	75	75	75
	95th+12mmHg	124	124	125	126	128	129	130	86	86	87	87	87	87	87
10	Height (cm)	129.7	132.2	136.3	141	145.8	150.2	152.8	129.7	132.2	136.3	141	145.8	150.2	152.8
	90 th	109	110	111	112	113	115	116	72	73	73	73	73	73	73
	95 th	113	114	114	116	117	119	120	75	75	76	76	76	76	76
	95th+12mmHg	125	126	126	128	129	131	132	87	87	88	88	88	88	88
11	Height (cm)	135.6	138.3	142.8	147.8	152.8	157.3	160	135.6	138.3	142.8	147.8	152.8	157.3	160
	90 th	111	112	113	114	116	118	120	74	74	74	74	74	75	75
	95 th	115	116	117	118	120	123	124	76	77	77	77	77	77	77
	95th+12mmHg	127	128	129	130	132	135	136	88	89	89	89	89	89	89
12	Height (cm)	142.8	145.5	149.9	154.8	159.6	163.8	166.4	142.8	145.5	149.9	154.8	159.6	163.8	166.4
	90th	114	115	116	118	120	122	122	75	75	75	75	76	76	76
	95th	118	119	120	122	124	125	126	78	78	78	78	79	79	79
	95th+12mmHg	130	131	132	134	136	137	138	90	90	90	90	91	91	91

From 2017 (American Academy of Pediatric) Clinical Practice Guidelines, Table 5, Females, see References

